## CONFIDENTIAL

217884 (FLU SV MRNA-002)

Protocol Amendment 2 Final

Objectives	Endpoints (population summary)
	
For participants in Phase 1:
 
Safety laboratory:
 
 
Shift from a non-clinically significant laboratory value on Day 1 (pre-dose) to a clinically significant abnormal laboratory value on Day 8 (post-dose) and/or Day 29 (post-dose) for hematology and clinical chemistry (percentage of participants).
 

To evaluate the humoral immune response induced by the investigational study intervention	
 
CC1 antibody titer at Day 29 (GMT)
 
Fold increase in CC1 antibody titer from Day 1 to Day 29 (GMI)
 
CC1 seroconversion from Day 1 to Day 29 (SCR)
 
CC1 seroprotection at Day 1 and Day 29 (SPR)
 
CC1 antibody titer at Day 29 (GMT)
 
Fold increase in CC1 antibody titer from Day 1 to Day 29 (GMI)
 
CC1 seroconversion from Day 1 to Day 29 (SCRt)
 

	
Secondary
 
 
CC1 antibody titer at Day 92 and Day 183 (GMT)
 
Fold increase in CC1 antibody titer from Day 1 to Day 92 (GMI)
 
Fold increase in CC1 antibody titer from Day 1 to Day 183 (GMI)
 
CC1 seroprotection at Day 183 (SPRt)
 
CC1 antibody titer at Day 92 and Day 183 (GMT)
 
Fold increase in CC1 antibody titer from Day 1 to Day 92 (GMI)
 
Fold increase in CC1 antibody titer from Day 1 to Day 183 (GMI)
 

	
Tertiary
 
CC1

Objectives	Endpoints (population summary)
CC1	

Endpoints are designed for all the participants, unless indicated otherwise in the table.

AE: adverse event; SAE: serious adverse event; AESI: adverse events of special interest; MAE: medically attended event; SCR: seroconversion rate; SPR: seroprotection rate; CCI [REDACTED]

GMI: geometric mean increase;

GMT: geometric mean titers; MN: microneutralization; CCI [REDACTED]; CCI [REDACTED]

\* Refer to Section 8.4.1 for the list of safety events and timeframe for collection.

† Refer to Section 9.3.2 for definition of SCR and SPR.

[figure not shown]
Details related to attributes of estimand covering intercurrent events, population and treatment definition are provided in the Section 9.

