### 9.3.2. Co-primary and secondary immunogenicity endpoints

At each phase, the group difference between the investigational study intervention formulation, and dose level and the control group will be assessed separately as follows for CCI [REDACTED]:

- At each post-dosing timepoint separately, the 2-sided CI for group GMT ratio between investigational study intervention dose and (over) the control group will be derived from an ANCOVA model on  $\log_{10}$  transformed concentration. The ANCOVA model will include group (i.e., each of the investigational study intervention and the control group), actual age of participants, country, flu vaccination history and  $\log_{10}$ -transformed concentration at pre-dosing as fixed effects. The adjusted GMT and GMI in each group will be obtained from the same model with 95% CI. Missing data will not be replaced. Concentrations below the assay lower level of quantification (LLOQ) will be replaced by half the assay LLOQ.
- For a given age group, the 2-sided 95% CI on group difference in SCR between an investigational study intervention and (minus) the control group will be computed at Day 29 based on the method of Miettinen and Nurminen [Miettinen, 1985].
- For CCI [REDACTED] only: the percentage of participants achieving seroprotection, defined as having post-dosing CCI [REDACTED] will be summarized by age group with associated exact 95% CI.

All analyses will be performed separately for each age group, where applicable.

Abbreviation/term	Definition
GMI	The geometric mean of the ratios of the post-dosing titer over the Day 1 titer.
CCI	The percentage of dosed participants who have either a pre-dose CCI [REDACTED] and a post-dosing CCI [REDACTED] or a pre-dose CCI [REDACTED] and at least a 4-fold increase in post-dosing CCI [REDACTED].
	The percentage of dosed participants who have either a pre-dose CCI [REDACTED] and a post-dosing CCI [REDACTED] or a pre-dose CCI [REDACTED] and at least a 4-fold increase in post-dosing NI titer.
SPR (seroprotection rate)*	The percentage of dosed participants with a CCI [REDACTED].
S+ (seropositive)	Titer $\geq$ LLOQ

CCI [REDACTED]

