2	Refer to 1	To evaluate the humoral immune response induced by the investigational study intervention	
 CCI [REDACTED] at Day 29 (GMT) Fold increase in [REDACTED] from Day 1 to Day 29 (GMI) [REDACTED] from Day 1 to Day 29 (SCR) CCI [REDACTED] at Day 1 and Day 29 (SPR) CCI [REDACTED] at Day 29 (GMT) Fold increase in [REDACTED] from Day 1 to Day 29 (GMI) CCI [REDACTED] from Day 1 to Day 29 (SCR^t) 	
a. Vaccination administration errors.
 
b. Taken prohibited medication or vaccination prior to Day 29 blood draw.
 
c. Medical condition forbidden by protocol (i.e., either a confirmed immunodeficiency condition, new malignancy, or development of confirmed influenza disease) prior to
	
Hypothetical strategy: data from participant after ICE will be excluded from the analysis.
	
 Between-group geometric mean titer (GMT) ratio (Flu mRNA candidate over Comparator) with 95% confidence interval (CI) Within-group geometric mean increase (GMI) with 95% CI Between-group difference in seroconversion rate (SCR³) (Flu mRNA candidate minus Comparator) with 95% CI Between-group difference in seroprotection rate (SPR³) (Flu mRNA candidate

Ref #	Population	Objectives	Variable (Endpoint)	Intercurrent event (ICE) ²		Population level summary
				Description	Handling strategy	
				Day 29 blood draw. d. Blood sample collected for Day 29 out of window		minus Comparator) with 95% CI
Secondary						
2	Refer to 1	To evaluate the humoral immune response induced by the investigational study intervention	
 • CCI at Day 92 and Day 183 (GMT) • Fold increase in CCI CCI from Day 1 to Day 92 (GMI) • Fold increase in CCI CCI from Day 1 to Day 183 (GMI) • CCI CCI at Day 183 (SPRt) • CCI at Day 92 and Day 183 (GMT) • Fold increase in CCI CCI from Day 1 to Day 92 (GMI) Fold increase in CCI CCI from Day 1 to Day 183 (GMI)	Refer to 2	Refer to 2	Refer to 2

Endpoints are designed for all the participants, unless indicated otherwise in the table.

[figure not shown]
AE: adverse event; AESI: adverse event of special interest; CI: confidence interval; GMI: mean geometric increase; GMT: geometric mean titer; CCI CCI ; ICE: intercurrent event; MAE: medically attended event; CCI CCI , SAE: serious adverse event; SCR: seroconversion rate; SPR: seroprotection rate; YOA: years of age.

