3. ANALYSIS SETS

Analysis Set	Definition / Criteria	Analyses Evaluated
Screened	All participants who were screened for eligibility.	Screening failure
Enrolled	All participants who entered the study (who were randomized or received study intervention or underwent a post-screening study procedure). Note: screening failures (who never passed screening, even if rescreened) and participants screened but never enrolled into the study (met eligibility but not needed) are excluded from the Enrolled analysis set as they did not enter the study.	Study population
Exposed Set (ES)	All participants who received a study intervention. Analysis per group is based on the study intervention administered.	Safety, immunogenicity if applicable, demography
Per Protocol Set (PPS)	All eligible participants who received the dose of study intervention as per protocol, had immunogenicity results pre- and Day 29 post-dosing for at least one CCI [REDACTED], without intercurrent conditions (influenza disease, new malignancy and immunocompromised condition) that may interfere with immunogenicity and without prohibited concomitant medication/vaccination before Day 29. The analysis will be done according to the study intervention that participants received. Results from blood sample deviating from the dosing/blood draw intervals (refer to Table 9 and Table 10) as well as results obtained after intercurrent conditions (influenza disease, new malignancy and immunocompromised condition) that may interfere with immunogenicity or after prohibited concomitant medication/vaccination during this period will be excluded from the PPS.	Immunogenicity, demography

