4.2.2. Co-primary and Secondary Immunogenicity Endpoints

At each phase and for OA and YA separately, the group difference between each mRNA group and the control group will be assessed separately as follows for **CCI** [REDACTED]

- At each post-dosing timepoint separately, the 2-sided CI for group GMT ratio between investigational study intervention dose and (over) the control group will be derived from an ANCOVA model on log10 transformed concentration. The ANCOVA model will include group (i.e., each of the investigational study intervention and the control group), actual age of participants, country, flu vaccination history and log10-transformed concentration at pre-dosing as fixed effects. The adjusted GMT and GMI in each group will be obtained from the same model with 95% CI. Missing data will not be replaced. Concentrations below the assay lower level of quantification (LLOQ) will be replaced by half the assay LLOQ.
- For a given age group, the 2-sided 95% CI on group difference in SCR between an investigational study intervention and (minus) the control group will be computed at Day 29 based on the method of Miettinen and Nurminen [Miettinen, 1985].
- CCI** [REDACTED]
[REDACTED]
[REDACTED]

All analyses will be performed separately for each age group, where applicable.

Abbreviation/term	Definition
GMI	The geometric mean of the ratios of the post-dosing titer over the Day 1 titer.
CCI [REDACTED] [REDACTED]	The percentage of dosed participants who have either a CCI [REDACTED] and a post-dosing CCI [REDACTED] or a CCI [REDACTED] and at least a 4-fold increase in post-dosing CCI [REDACTED].
CCI [REDACTED] [REDACTED]	The percentage of dosed participants who have either a CCI [REDACTED] and a post-dosing CCI [REDACTED] or a pre-dose CCI [REDACTED] and at least a 4-fold increase in post-dosing CCI [REDACTED].
CCI [REDACTED] [REDACTED]	The percentage of dosed participants with a CCI [REDACTED]
S+ (seropositive)	Titer \geq LLOQ

The following SAS code will be used for computation of GMT ratio where AVAL and BASE are the \log_{10} transformed GMC values at pre-dose and post-dose respectively, while country and vaccination history are the minimization factors at randomization:

```
PROC GLM DATA=immuno ALPHA=0.05;
  CLASS trt01a country vacchist;
  BY agecat strain;
  MODEL aval = trt01a country vacchist base age;
  LSMEANS trt01a / CL;
RUN;
```

For the purpose of analysis, previous flu vaccination history reported as 'Unknown' will be classified as 'No'.

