The SCR will be computed using the following SAS code where AVALC is the seroconversion status post-dose:

```
PROC FREQ DATA=immuno;
  BY agecat strain;
  TABLE trt01a*avalc / RISKDIFF (CL=MN) ALPHA=0.05;
RUN;
```

The assays used in this study and their LLOQs are presented in [Table 3](#).

Table 3 Assay cut-off values for various assays in Phase 1

Assay	Unit	Test ID	LLOQ
CCI			

Table 4 Assay cut-off values for various assays in Phase 2

Assay	Unit	Test ID	LLOQ
CCI			

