6.2.4.2. Standardized Asymptotic Confidence Intervals Around Differences in Proportions

The standardized asymptotic confidence intervals around differences in proportions are derived using the method of Miettinen and Nurminen. [[Miettinen](#), 1985]

[figure not shown]
CONFIDENTIAL

217884

CCI

[figure not shown]

CCI

Instructions – General Principles of Scoring

[figure not shown]
CCI

[figure not shown]
CONFIDENTIAL

217884

CCI

CCI

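### The planned mRNA-minus-control seroprotection difference shows no baseline adjustment in the readable text, although the pre-dose titre is collected and already used for the GMT ratio; the cost is some precision, usually a few percent of interval width

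*Protocol*

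**What the plan says.** Protocol Table 5 (section 3) has "seroprotection at Day 1 and Day 29 (SPR") as a co-primary immunogenicity endpoint, with SPR at Day 183 as secondary. The between-group contrast appears only in SAP Table 2 (section 1.1.1), whose population-level summary for the humoral estimand includes "Between-group difference in seroprotection rate (SPR³) (Flu mRNA candidate" minus comparator, with a 95% CI. No covariate is named there.

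On method, the readable text says this:

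- Protocol 9.3.2: the percentage seroprotected "will be summarized by age group with associated exact 95% CI". No between-group SPR contrast is described.
- SAP 4.2.2: the third bullet, in the position of the protocol's SPR bullet, is redacted.
- SAP 6.2.4.2: "The standardized asymptotic confidence intervals around differences in proportions are derived using the method of Miettinen and Nurminen". No strata are mentioned.
- SAP 4.2.2 code: "TABLE trt01a*avalc / RISKDIFF (CL=MN) ALPHA=0.05". This is an unstratified two-way table, introduced for SCR and not for SPR.

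By contrast, the GMT and GMI ANCOVA in SAP 4.2.2 includes age, country, flu vaccination history and "log10-transformed concentration at pre-dosing as fixed effects". Randomization (protocol 6.3, SAP 1.2) minimizes on flu vaccination history, country, center and study, but not on pre-dose titre or serostatus.

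The SAP section 3 PPS requires that a participant "had immunogenicity results pre- and Day 29 post-dosing for at least one" item, whose name is redacted.

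**The concern.** Seroprotection is a threshold applied to a titre. A participant above the threshold before dosing will probably be above it at Day 29 whichever vaccine was given, so Day 1 status explains part of the Day 29 variation that has nothing to do with the vaccine. The plan treats the pre-dose titre as prognostic when the outcome is the log titre, but the readable text does not use it when the same titre is dichotomized.

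The study tests no hypothesis, so interval width is what the analysis delivers, and SAP 1.2 says that the Phase 2 interim analysis will inform Phase 3 preparation. The risk difference is collapsible, so adjusting for baseline need not change the quantity being estimated. What is at stake is precision, and the share of the Day 29 difference that reflects chance imbalance at Day 1.

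There is also a wording point. Table 2 sets a generic SPR difference against an endpoint line that includes Day 1, and a pre-dose difference between randomized arms can reflect only chance.

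**Working it through.** **The plan's own precision figure.** SAP 5.2 gives 108 evaluable per group, SD 0.5 on the log10 scale and a 1.36-fold half-width. Check: 10^(1.96 × 0.5 × √(2/108)) = 10^0.1334 = 1.359. Enrolment: 108/(1 − 0.10) = 120. Both reproduce. No precision figure for SPR is readable.

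**Assumptions.** The documents give no Day 1 SPR, Day 29 SPR, retention, conversion or Day 1/Day 29 correlation. Two models are used, each over a range, at n = 108 per group.

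**Model A: bivariate normal log10 titres.** Day 1 SPR is 20–80%, Day 29 SPR 70–95% and the log-titre correlation r 0.3–0.7.

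- Crude half-width = 1.96 × √(2p(1−p)/108). At p = 0.80 this is 1.96 × √0.002963 = 10.67 points.
- Half-width after stratifying on Day 1 status = crude × √(1 − φ²), where φ is the Day 1/Day 29 serostatus correlation. In the mid case (Day 1 40%, Day 29 80%, r = 0.5), φ² = 0.068, so 10.67 × √0.932 = 10.30 points. That is 3.5% narrower, equivalent to 1/0.965² − 1 ≈ 7% more participants.
- Over the whole grid the reduction is 0.3% to 12.0%, or 0.02 to 1.5 points.
- Adjusting for the continuous log10 pre-dose titre instead gives 1.1% to 17.0%, with 6.9% in the mid case.

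**Model B: retention and conversion.** Let p0 be Day 1 SPR, ret the proportion of those still protected at Day 29, and c the proportion of the others who convert. Per arm:

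- p = p0·ret + (1 − p0)·c, with crude variance p(1 − p);
- within-stratum variance = p0·ret(1 − ret) + (1 − p0)·c(1 − c).

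The large-sample SD ratio is the square root of (within-stratum variance summed over arms) / (crude variance summed over arms). For p0 = 0.4, ret = 0.98 and c = 0.70/0.55, p is 0.812 and 0.722, the sums are 0.2902 and 0.3534, and the ratio is 0.906. Simulation (40,000 trials, Mantel-Haenszel weights) includes the finite-sample loss:

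| Day 1 SPR | Retention | Conversion, mRNA/control | Crude SD (points) | Stratified SD (points) | Narrower |
|---|---|---|---|---|---|
| 40% | 98% | 70/55% | 5.7 | 5.2 | 9% |
| 50% | 98% | 75/60% | 5.1 | 4.7 | 8% |
| 30% | 98% | 60/50% | 6.3 | 5.8 | 9% |
| 60% | 98% | 60/50% | 5.3 | 4.5 | 15% |
| 40% | 98% | 70/70% | 5.3 | 5.0 | 6% |
| 40% | 98% | 90/70% | 4.5 | 4.3 | 3% |
| 40% | 95% | 90/70% | 4.7 | 4.6 | 2% |
| 30% | 98% | 85/85% | 4.3 | 4.2 | 2% |
| 40% | 98% | 90/90% | 3.4 | 3.4 | 1% |

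The large-sample ratio in the fourth row is 0.842, which gives the upper end of about 16%. The mean difference is the same crude and stratified (first row: 9.0 points each). With 24 per group, as in Phase 1, the last row's SD ratio is 1.00, so there is no gain.

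**Chance imbalance.** The SD of the Day 1 SPR difference under simple randomization is √(2 × 0.4 × 0.6/108) = 6.7 points. In the Model A mid case, Day 29 SPR is 92.8% in those protected at Day 1 and 71.5% in the others, so one SD of imbalance moves the Day 29 difference by 0.213 × 6.7 ≈ 1.4 points. Over the grid this is 0.2 to 3.0 points.

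**Validity.** In 10,000 simulated trials per scenario, the crude difference had bias below 0.1 point and coverage of 94.4–94.7%. The stratified difference had coverage of 94.2–94.7%.

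**The case against.** The strongest reply is that the SAP's SPR bullet is blacked out, so the absence of adjustment there cannot be shown, and the PROC FREQ code is for SCR. That stands as a limit on the reading. It does not remove the point: the corresponding protocol bullet is readable and crude, SAP 6.2.4.2 names no strata, and Table 2 names no covariate.

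Second, the crude interval is already valid and its 95% coverage allows for chance imbalance. That stands in full. Minimization on vaccination history may also make the Day 1 imbalance smaller than the simple-randomization figure.

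Third, the size depends on inputs that nobody can read from the documents. That also stands. A reader might take 8 to 16% as the typical gain, but it needs near-complete retention and only moderate conversion.

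Fourth, a reader might assume that Day 1 serostatus is known for everyone in the PPS. The SAP requires paired results for at least one redacted item only, so a participant may lack a Day 1 result for a given strain or readout.

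Fifth, a reader might infer that the SAP plans a treatment comparison at Day 1. Table 2 pools generic summaries over several endpoints and does not say so specifically; this is a matter of wording.

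Finally, GMT and SPR could differ for reasons other than baseline adjustment: one is a mean, the other a proportion above a threshold, and the ANCOVA has further covariates. Such a disagreement would not by itself show a fault.

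**Conclusion.** The point holds as a modest precision improvement. On the readable text the SPR difference is unadjusted, and a prognostic baseline value that the plan already uses elsewhere is left out. At 108 per group the crude interval is about 0 to 16% wider than a Day 1-stratified one. A few percent is typical, and about 1 to 3% applies once 85–90% of those not protected at Day 1 convert in both arms, or 90% against 70%. These ranges rest wholly on assumed Day 1 SPR, retention and conversion.

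The documents do not support a claim of bias or an invalid interval. No readable decision rule depends on SPR, and the study is descriptive. In Phase 1, with 24 per group, the gain can disappear.

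**What to change.** 1. In SAP 4.2.2, state the method for the SPR difference. For the Phase 2 post-dose contrasts (Day 29 and Day 183), add one baseline-adjusted difference, named in advance. Either use a standardized risk difference after logistic regression on group and pre-dose log10 titre, which recovers more precision in Model A, or stratify by Day 1 serostatus with a score-type interval (for example the COMMONRISKDIFF option of PROC FREQ).
2. Restrict this analysis to participants with a Day 1 result for the strain concerned, and report how many are dropped.
3. Keep the crude percentages with exact intervals and the crude Miettinen-Nurminen difference alongside. Keep the crude analysis alone for the Phase 1 groups of 24.
4. In SAP Table 2, say that the SPR contrast applies to post-dose visits and that Day 1 SPR is descriptive. Align protocol 9.3.2 if it is amended for other reasons.

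The cost is a few sentences and a few lines of code, with no new data, visits or participants. The downsides are sparse strata or strata near 100%, where the score interval or the crude result has to serve, and the loss of the few participants without a Day 1 result for a given strain.

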## 4. STUDY DESIGN

### 4.1. Overall design

Refer to [Figure 1](#) and [Figure 2](#) (Section 1.2) for the overview of study design.

- Multi-country, multi-center.
- Self-contained.
- All study interventions are administered as single-dose intramuscularly (IM).
- Active control:

- Intended duration of the study per participant: Up to 7 months for participants enrolled in Phase 1 (screening period included) and 6 months for participants enrolled in Phase 2 of the study.
- Aspects of data collection: blood samples, safety events, CCI ██████████ ██████████.
- Method of data collection:
  - Standardized electronic Case Report Form (eCRF)
  - Solicited AEs, the occurrence of unsolicited AEs and responses to CCI ██████████ will be collected using an electronic Diary (eDiary); participants, with support from the site, may install the eDiary application on their own personal, handheld device (e.g., mobile phone, tablet) or the site may provide a device that is pre-programmed with the eDiary.
- Safety monitoring: the review of safety data will be performed by an internal Safety Review Team (**SRT**) and internal Safety Review Committee (iSRC). Refer to Section [8.3.7.1](#) for more information on safety monitoring strategy applicable to this study and Section [10.1.6](#) for **SRT** and iSRC composition and role.

- Dose selection for Phase 2: refer to Section [4.3.2](#) for detailed information on dose selection by an internal Data Review Committee (iDRC) and Section [10.1.6](#) for iDRC composition and role.

**Phase 1:**

- Participants aged 18-50 years.
- 13 groups enrolled in parallel (12 mRNA groups and 1 control group), detailed in [Table 6](#).
- Approximate number of participants: 312 (24 participants per group).
- Blinding: single-blind. Refer to Section [6.4](#) for more information on blinding.
- Study interventions administered in Phase 1 will be manufactured as separate components and mixed at site by the site staff/pharmacist based on the scheme provided in the [Table 6](#), before dosing each participant. This approach will only be applicable in the Phase 1 part.

**Table 6** Potential study interventions composition (Phase 1)

Study groups	Study interventions*	CCI
Flu mRNA_1_1	F2C22C/DL001Z	
Flu mRNA_1_2	F2B22A/DL001Z	
Flu mRNA_1_3	F2B22B/DL001Z	
Flu mRNA_1_4	F2B22C/DL001Z	
Flu mRNA_1_5	F2B22D/DL001Z	
Flu mRNA_1_6	F2B22E/DL001Z	
Flu mRNA_1_7	F2F22A/DL001Z	
Flu mRNA_1_8	F2F22B/DL001Z	
Flu mRNA_1_9	F2F22C/DL001Z	
Flu mRNA_1_10	F2F22D/DL001Z	
Flu mRNA_1_11	F2F22E/DL001Z	
Flu mRNA_1_12	F2F22F/DL001Z	
Control	CCI	

\* Strains used to design study interventions are based on WHO recommendation for influenza virus vaccine composition for the 2022-2023 NH season.

\*\* CCI : GSKVx00000034792; CCI : GSKVx00000040033; CCI : GSKVx00000034794; CCI : GSKVx00000034795; CCI : GSKVx00000034796; CCI : GSKVx00000034797; CCI : GSKVx00000034798; CCI : GSKVx00000039711. Refer to Section 4.3 for information on selection of doses and combinations and Section 6.1 for details on study interventions.

